I have read the protocol, including all appendices, and I agree that it contains all the necessary information for me and my personnel to conduct this study as described. I will conduct this study as outlined herein, in accordance with the regulations stated in the Federal Code of Regulations for Good Clinical Practices and International Conference on Harmonisation guidelines and will make a reasonable effort to complete the study within the time designated.

I will provide all study personnel under my supervision copies of the protocol and any amendments, and access to all information provided by Neurotech Pharmaceuticals, Inc., or specified designees. I will discuss the material with them to ensure that they are fully informed about NT-501 and the study.

Principal Investigator Name (printed)	Signature
	Signature
Date	Site Number

Confidential

PROTOCOL SYNOPSIS

Title of Study:	Phase II, Multicenter, Open-label Safety Study of Bilateral NT-501 in Participants with Macular Telangiectasia Type 2			
IND Number:	10931			
Sponsor:	Neurotech Pharmaceuticals, Inc.			
Study Compound:	NT-501 is a combination of a sealed semipermeable hollow fiber membrane (HFM) capsule surrounding a scaffold of 6 strands of polyethylene terephthalate (PETP) yarn, and Ciliary Neurotrophic Factor (CNTF) secreting NTC-201.6A cells that adhere to the polyethylene terephthalate (PET) yarn. Using a surgical procedure, this implant is positioned into the vitreous and anchored to the sclera			
Study Objectives				
Primary Objective:	Assess the incidence and severity of adverse events following bilateral ocular implantation of NT-501. Ocular safety will be assessed using ocular examinations, as well as best corrected visual acuity (BCVA) measurements using the Early Treatment Diabetic Retinopathy Study (ETDRS) visual acuity protocol. Systemic safety will be assessed based on the incidence and severity of systemic adverse events (AE)			
Secondary Objectives:	Assess serum levels of CNTF, the immunogenicity of NT-501 with quantification of antibodies (Ab) to CNTF, neutralizing antibodies (Nab) to CNTF, and Ab to NTC-201.6A cells, as well as Ab to dihydrofolate reductase (DFHR), in samples collected at the Baseline, Month 1, Month-3 and Month-6 study visits.			
Study Design:				
Clinical Study Sites:	Participants will be recruited from up to 10 clinical study sites. Clinical sites must have participated in the multicenter Phase 1/2 extension study, NTMT-01/02E, or the Phase 3 (NTMT-03) study of NT-501 in participants with Macular Telangiectas Type 2 (MacTel).			
Number of Participants:	The goal is to have a minimum of 30 evaluable participants			
Structure:	Multicenter, Open-Label			
Visit Schedule:	There will be a maximum of 7 visits over a study period of up to 7 months. These visits will include Visit 1, Screening (Day -28 to Day -1); Visit 2, Surgery; Visit 3, Post-Surgery Day 1; Visit 4, Post-Surgery Week 1; Visit 5, Post-Surgery Month 1; Visit 6, Post-Surgery Month 3; Visit 7, Post-Surgery Month 6 and Exit Visit.			
Duration:	The study duration will be approximately 7 Months (screening period of up to 28 days plus a follow-up period of 6 months).			

Study Description:	This is a multicenter, open-label, study to evaluate the safety of bilateral NT-501 implants in a minimum of 30 study participants with MacTel type 2. All study subjects who have received a NT-501 implant in one eye through participation in the Phase 1/2 extension study, NTMT-01/02E, or the Phase 3 (NTMT-03) study and meet the eligibility criteria, will receive a NT-501 implant in their fellow eye and will be followed for 6 months following the NT-501 implantation.			
Inclusion Criteria:	Study eligibility is to be assessed at Visit 1 (Screening). To participate in this study, the potential participant must meet all the following criteria:			
General Inclusion Criteria: Ocular Inclusion Criteria	 Participants from the Phase 3 study must have completed the Month-24 visit Participant in the MacTel Phase 1/2 extension study or the Phase 3 study must exit these studies prior to entering the Bilateral Implant safety study (NTMT-02B) Participant must be willing and able to follow the study instructions and be willing and able to complete all required study procedures and visits Participant must be willing and able to provide a signed Informed Consent, as well as written documentation in accordance with the relevant country and local privacy requirements, e.g., written data protection consent Females of childbearing potential must consent to and complete a pregnancy test during the screening visit A participant's refusal to allow the collection of blood samples for Ciliary neurotrophic factor (CNTF), Ab to CNTF, Nab to CNTF, Ab to NTC-201.6A cells, and Ab to DFHR will not exclude the participant from study participation Participant must have a positive diagnosis of MacTel type 2, with evidence of fluorescein leakage typical of MacTel, and at least one of the other features that include hyperpigmentation that is outside of a 500-micron radius from the center of the fovea, retinal opacification, crystalline deposits, right-angle vessels, or inner/outer lamellar cavities in their study eyes Participant must have a NT-501 implant in one eye and have completed the Phase 1/2 extension study (NTMT-01/-2E) or the Month 24-visit of the Phase 3 study (NTMT-03) 			
Exclusion Criteria	Unless otherwise stated, eligibility assessments are to be performed at Visit 1 (Screening). The following criteria will exclude participant from entry into the study.			
General Exclusion Criteria	 Females of childbearing potential (those who are not surgically sterilized or post- menopausal, i.e., absence of menstruation for 12 months or longer) may not participate in the study if any of the following conditions exists: Pregnant (positive pregnancy test at Visit 1 or intend to become pregnant during the study) Nursing (lactating) Do not agree to use adequate birth control methods for the duration of the study and until 90 days after the last administration of study drug 			

(adequate birth control methods are: hormonal – oral, implantable, transdermal or injectable contraceptives; mechanical – spermicide in conjunction with a barrier such as condom or diaphragm, intrauterine device [IUD] or surgical sterilization of partner, or total sexual abstinence)

- 2. Participant is too ill to likely complete the entire study, based on the investigator's assessment
- 3. Participant, in the opinion of the investigator, is not suitable for study participation
- 4. Participant has any screening laboratory result (serum chemistry, hematology, urinalysis) that in the opinion of the investigator is not suitable for study participation
- 5. History or current evidence of severe hypersensitivity to the NT-501 implant
- 6. Participant has a history or current evidence of a medical condition (systemic or ophthalmic disease, metabolic dysfunction, physical examination finding or clinical laboratory finding) that may in the opinion of the investigator preclude the safe administration of the NT-501 or adherence to the scheduled study visits, safe participation in the study or affect the results of the study (e.g., unstable or progressive cardiovascular, cerebral vascular, pulmonary, Parkinson's, liver or renal disease, depression, cancer, or dementia)
- Ocular Exclusion Criteria 1. Participant has a history or evidence of the following surgeries/procedures in the study eye, as assessed at Visit 1, including:
 - Submacular surgery
 - Vitrectomy
 - Retinal detachment
 - Incisional glaucoma surgery
 - o Trabeculectomy or trabeculoplasty
 - Cataract surgery or laser-assisted in situ keratomileusis (LASIK) performed in the previous 6 months
 - 2. Participant has uncontrolled glaucoma; or ocular hypertension, i.e., $IOP \ge 25$ mmHg in the study eye
 - 3. Participant has evidence of intraretinal or subretinal neovascularization or central serous chorio-retinopathy in the study eye
 - 4. Participant has evidence of ocular disorder(s) in the study eye of a severity that could confound the interpretation of study results, compromise visual acuity or require medical or surgical intervention during the study period, including retinal vascular occlusion, severe non-proliferative or proliferative diabetic retinopathy, retinal detachment, macular hole, geographic atrophy, intraretinal or subretinal neovascularization, central serous chorio-retinopathy, pathological myopia
 - 5. Participant has a vitreous hemorrhage in the study eye at Visit 1 (Screening)
 - 6. Participant has the spherical equivalent of refractive error in the study eye demonstrating more than 8 diopters of myopia
 - 7. Participant has a history or evidence of penetrating ocular trauma in the study eye
 - 8. Participant has an anticipated need for cataract extraction in the study eye within 6 months of Visit 1 (Screening) such as cortical opacity > standard 3, posterior

subcapsular opacity > standard 2, or a nuclear opacity > standard 3 as measured on the Age-Related Eye Disease Study (AREDS) clinical lens grading system

- 9. Participant has uveitis, history of uveitis in either eye or history of ocular herpes virus in either eye
- 10. Participant has undergone major surgery within the last 6 months (systemic or ocular in either eye) or participant who is likely to require major surgery within 6 months of Visit 1 (Screening)
- Participant has a periocular or ocular/intraocular infection or inflammation in either eye (such as infectious conjunctivitis, keratitis, scleritis, endophthalmitis) within 3 months prior to Visit 1 (Screening)
- 12. Participant has ocular hypotension in either eye (<6 mmHg) that in the opinion of the Investigator would interfere with the NT-501 implantation
- 13. Participant has a history of scleritis, scleral thinning, periocular, ocular, or intraocular infection or inflammation, cicatrizing conjunctival diseases any other ocular conditions in the study eye that could interfere with the administration of NT-501

Response Measures

- Adverse Events after NT-501 Implantation Surgery
- General Physical Exam
- Vital Signs
- Pregnancy Test
- Complete ophthalmic exam (consisting of an external examination of the eye and adnexa, screening for eyelid/pupil responsiveness, slit lamp biomicroscopy, dilated fundus examination, indirect ophthalmoscopy, and IOP)
- BCVA
- SD-OCT
- Serum chemistry, hematology, and urinalysis
- Ab and Nab to CNTF, Ab to NTC-201.6A cells and Ab to DFHR (serum)
- Blood sample collection for analysis of serum levels of CNTF

Safety Endpoints

Number and proportion of adverse events from day of surgery through post NT-501 implantation follow-up

Number and proportion of severe adverse events from day of surgery through post NT-501 implantation follow-up

Number and proportion of ocular adverse events from day of surgery through post NT-501 implantation follow-up

Number and proportion of non-ocular adverse events from day of surgery through post NT-501 implantation follow-up

General Statistical Methods
and Types of AnalysesFormal sample size calculations were not performed. The number of participants was
chosen based on feasibility and is considered sufficient to meet the study objectives.

The general analytical approach for all endpoints is descriptive. No formal statistical hypothesis testing will be conducted.

Safety Population: Defined as participants who have a NT-501 implant in both eyes. This population will be used for all safety analysis.

Safety Analysis

Analysis Populations

The primary objective of the study is to assess the safety and tolerability of bilateral NT-501 implants. Tolerance and safety will be based on the incidence and severity of treatment-emergent adverse events (TEAEs).

Sample size CalculationsFormal sample size calculations were not performed. The number of participants was
chosen based on feasibility and is considered sufficient to meet the study objectives

Figure 1. Study Design

Confidential

NTMT-02B_Protocol_v4.0_21JAN2022 | VV-TMF-136134 | 1.0

NTMT-02B – Bilateral NT-501 Implant Phase 2 Study Protocol Version 4.0 (21 January 2022)

Table 1: Schedule of Visits and Procedures in the Assessment of Safety in Participants with Bilateral NT-501 Implants

Procedures	Screening	Surgery	Post-	Post-	Post-	Post-Surgery Month	Post-
	Day	Day 0	Surgery	Surgery	Surgery	3	Surgery
	-28 to -1	2	Day 1	Week 1	Month 1		Month
			-				6
Visit Window				±2 days	±7days	± 14 days	± 14
							days
Visit Number	1	2	3	4	5	6	7
STUDY DAY	-28 to -1	0	1	7	30	90	180
Informed Consent	Х						
Demographics	X						
Medical & Ophthalmic	Х	Х					
History ^a							
Concomitant Medications	Х	Х	Х	X	Х	Х	Х
and non-study procedures							
Adverse Events		X	X	X	X	X	X
Vital Signs ^b	X						
Inclusion/exclusion	X						
criteria							
Eligibility Review	Х	Х					
Medical evaluation ^c	Х	Х					
Pregnancy Test ^d	Х						
Serum Chemistry,	Х						
Hematology & Urinalysis							
Visual Acuity (BCVA)	OUe	SEf		SEf	OU ^e	OU ^e	OU ^e
Measurement of pupil	OU				OU	OU	OU
diameter							
Complete Ophthalmic	OU		SE	SE	OU	OU	OU
Exam ^g							
Dilated Fundus	OU		,				OU
Photography			×	GE	OU	011	011
SD-OCT "	OU			SE	00	OU	00
Fluorescein Angiography	00						
Serum concentrations of	Х				Х	X	Х
CNTF, Ab or Nab to							
CNTF, Ab to NTC-							
201.6A cells; or Ab to							
DFHR (serum)							
NT-501 implantation		X					
surgery			~-	~-		0	
Post NT-501 implant			SE	SE	OU	OU	OU
assessment					0.7.7	0.77	077
External photograph of					OU	OU	OU
conjunctiva over implant							
Complete Exit Form							X

Abbreviations: BCVA= Best Corrected Visual Acuity; SD-OCT = spectral domain optical coherence tomography, OU = both eyes, SE = study eye

- a Demographic data includes height, weight, eye color and smoking history
- b Vital signs include body temperature, pulse rate, respiration rate and sitting blood pressure
- c The medical evaluation may be performed during screening or on the day of surgery; the evaluation is standard for any surgical procedure or anesthesia (the tests performed will be site-specific)
- d Females of childbearing potential only; additional pregnancy tests may be performed at any time/day during study
- e Manifest refraction will be performed prior to BCVA assessments except for the BCVA assessments performed prior to surgery and 1 week following surgery
- f Best-corrected visual acuity must be performed within 1 week prior to the day of surgery
- g Complete ophthalmic exam consists of an external examination of the eye and adnexa, screening for eyelid/pupil responsiveness, slit lamp biomicroscopy, dilated fundus examination, indirect ophthalmoscopy, and IOP assessment) Slit lamp biomicroscopy, indirect ophthalmoscopy and intraocular pressure (IOP). IOP measurements will be taken prior to pupil dilation. If possible, IOP measurements should take place at approximately the same time of the day at each visit and with the same equipment
- ^h The same SD-OCT instrument should be used for an individual participant throughout the entire study

LIST OF ABBREVIATIONS

Ab	antibodies
AE	adverse event
AREDS	Age-Related Eye Disease Study
AMD	age-related macular degeneration
BCVA	best-corrected visual acuity
CFR	Code of Federal Regulations
CNTF	ciliary neurotrophic factor
CRA	clinical research associate
CRF	case report form
CRO	contract research organization
DHFR	dihydrofolate reductase
DSMC	data and safety monitoring committee
eCRF	electronic case report form
ECT	encapsulated cell therapy
EDC	electronic data capture
ETDRS	Early Treatment Diabetic Retinopathy Study
EZ	ellipsoid zone
FDA	Food and Drug Administration
GCP	Good Clinical Practice
HFM	hollow fiber membrane
ICF	informed consent form
ICH	International Conference on Harmonisation
IDE	investigational device exemption
IEC	independent ethics committee
IND	investigational new drug
IOP	intraocular pressure
IRB	institutional review board
IReST	International Reading Speed Texts
IS/OS	inner segment/outer segment junction line

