6.3.2 Visit 2: Enrollment and Surgery

If the participant meets all study criteria and agrees to participate in the study, then the implant surgery date should be identified. The implant surgery procedure should be completed within one month of the Screening visit.

On the date of the surgery, the investigator will confirm that no change in the participant's general condition has occurred that would exclude study participation.

The following evaluations/procedures will be conducted during this visit:

- Eligibility review
- Medical evaluation that is standard for any surgical procedure and its associated anesthesia (the specific tests to be ordered will be site-specific), unless the medical evaluation was performed during screening period
- Record any further medical/ophthalmic history
- Record any additional concomitant medications and non-study procedures
- Perform AE assessment (from the time surgery begins)
- Assess BCVA (may be performed within 1 week prior to the day of surgery or on the day of surgery, manifest refraction is not required)
- NT-501 implant surgery

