11 STATISTICS

11.1 General Procedures

This is an open-label Phase 2 study to evaluate safety of bilateral ocular NT-501 implants. The general analytical approach for all endpoints is descriptive. No formal statistical hypothesis testing will be conducted.

The safety population will include the data from all participants who receive a NT-501 implant in the study eye and have at least 1 safety measurement. No participant (or data) will be excluded from this dataset because of protocol violations that occur during the study.

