11.3 Statistical Methods

11.3.1 Analysis of Safety

Safety analyses will be performed on the safety population, which includes all participants who received an implant in the study eye. The assessment of safety will be based on the summary of ocular and nonocular treatment-emergent AEs (TEAEs) and ophthalmic examinations. The Medical Dictionary for Regulatory Activities (MedDRA) nomenclature will be used to code AEs.

Summaries for TEAEs will include the following: all TEAEs regardless of causality, treatment-related TEAEs, ocular TEAEs, treatment-related ocular TEAEs, TEAEs by intensity, SAEs, and TEAEs leading to discontinuation from the study.

The number and proportion of participants with a loss in BCVA of 15 or more letters from baseline in the study eye will be tabulated and presented. Summary tables will be supported with individual participant data listings.

Assessments of safety will also include measurements of systemic levels of CNTF, as well as the number of participants and the titer of antibodies to CNTF, neutralizing antibodies to CNTF and antibodies to NTC-201.6A that are observed at the 3-month time point and persist through the 6-month time point.

Descriptive statistics will be displayed to provide an overview of the safety results. For categorical parameters, these consists of the number and percent of participants in each category. The denominator for the percentages will be based on the number of participants appropriate for the purpose of the analysis. For continuous parameters, descriptive statistics includes n, mean standard deviation (SD), median, minimum, and maximum. Participants who prematurely discontinued the study will be evaluated on the basis of data collected at each visit attended.

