18.1 Premature Discontinuation

Premature discontinuation is not anticipated to be a frequent event based on the history of previous clinical trials with this implant. The investigator may discontinue a participant from the study if warranted and only after discussion with the medical monitor. If the participant discontinues study participation before completing the defined 6 months of follow-up, the principal investigator and study coordinator of the study site for the NHOR will be notified to ensure long-term follow-up.

If a participant requests explanation and withdrawal from the study, this can be readily arranged. The investigator should contact the sponsor's medical monitor to discuss the reasons for the request and discuss the procedure for explanation. If a participant discontinues from the study, they will not be replaced once recruitment is complete.

If a participant requests explanation but does not wish to withdraw from the study, this is also acceptable. The participant would continue in the study with all planned follow-up visits and assessments.

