2. SUBJECT POPULATION

2.1. Population Definitions

All analyses will be performed using the Safety Population.

- Safety Population: All subjects who receive a NT-501 implant in the study eye and have at least 1 safety measurement. No participant (or data) will be excluded from the safety population because of protocol violations that occur during the study.

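### The single Safety Population is worded inconsistently, and every wording leaves out a participant whose study-eye surgery starts but ends without an implant

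*Protocol*

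**What the plan says.** The SAP has a single analysis set: "All analyses will be performed using the Safety Population" (SAP 2.1). Its membership is described in four places, in three wordings.

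- **Protocol synopsis, Analysis Populations:** "Defined as participants who have a NT-501 implant in both eyes". No time point is attached to the verb.
- **Protocol 11.1:** "all participants who receive a NT-501 implant in the study eye and have at least 1 safety measurement". SAP 2.1 matches this: "All subjects who receive a NT-501 implant in the study eye and have at least 1 safety measurement".
- **Protocol 11.3.1:** "the safety population, which includes all participants who received an implant in the study eye", with no measurement condition.

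AE collection opens earlier than any of these allow for. Protocol 6.3.2 lists, for the surgery visit, "Perform AE assessment (from the time surgery begins". Protocol 9.1 records AEs from the time of surgery. The four primary endpoints in Protocol 3 and SAP 1.3.6 run from the day of surgery to six months.

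SAP section 5 reports no changes from the protocol's analyses, so nothing says which wording governs.

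**The concern.** This is a safety study of a surgically placed implant. Protocol 1.1.4 says most AEs seen so far were related to the implantation procedure, and Protocol 9.3 asks investigators to judge causality against the surgery separately from the implant and from CNTF. Harm from the procedure is therefore part of what the primary endpoints should capture.

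A denominator that requires a placed implant depends on how that procedure turned out. A surgery that is begun and then abandoned is plausibly one in which something went wrong. If it happens, the participant has AEs inside the collection window but belongs to no version of the analysis set, and any error in the tabulated rates is likely to be downward. With a planned minimum of 30 participants, one such case can decide whether a severe event appears in the primary table at all.

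**Working it through.** **1. Who is in under each wording**

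| Participant | Synopsis | Protocol 11.1 and SAP 2.1 | Protocol 11.3.1 |
|---|---|---|---|
| Implant placed and kept, at least one safety measurement | in | in | in |
| Implant placed, no safety measurement | in | out | in |
| Implant placed, later removed | unclear | in | in |
| Surgery started, no implant placed | out | out | out |

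The second row should be almost empty in practice, because AE assessment starts during the surgery visit and an eye examination follows on Day 1 (Protocol 6.3.3). The third row is in doubt only under the synopsis. The fourth row is the gap shared by every wording.

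**2. Whether the fourth row is dealt with elsewhere**

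- Protocol 4.1 and SAP 1.3.1 describe post-surgery visits for those who receive an implant.
- SAP 4.1 tabulates numbers screened, treated and withdrawn, with no count of surgeries started.
- SAP 4.5.1 counts exposure as those who received the study-eye implant.
- SAP 3.10 lists all data on the case report form, so the events would be visible in listings.

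The case is therefore handled in listings but not in the tables.

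**3. Size, for illustration**

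The documents state no power, alpha or calculated sample size, so there is no figure of the plan's own to reproduce. They also give no rate of surgery without implantation. Assume 31 surgeries are started, one ends without an implant and involves a severe AE, and no one else has a severe AE. Clopper-Pearson upper 95% limits, with x events in n participants, are the 0.975 quantile of Beta(x + 1, n − x).

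- All surgeries started: 1/31 = 3.2%, upper limit 16.7%.
- Population as written: 0/30 = 0%, upper limit 1 − 0.025^(1/30) = 11.6%.

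How often this could arise depends on an assumed rate p. The chance of at least one such case in 30 surgeries is 1 − (1 − p)^30:

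| Assumed p | Chance of at least one in 30 |
|---|---|
| 1% | 26.0% |
| 2% | 45.5% |
| 3% | 59.9% |
| 5% | 78.5% |

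These values of p have no source in the documents. The chances refer to any surgery without an implant, not to one with a severe event.

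**4. Whether redefining the population is enough**

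SAP 4.3 defines a new event as treatment-emergent only if onset falls after the day of implantation. SAP 3.2 calls that day Day 0. A new intraoperative event would therefore remain outside the tables even if the participant were added, and the example would give 0/31 (upper limit 1 − 0.025^(1/31) = 11.2%) rather than 1/31. This conflicts with the day-of-surgery start in Protocol 3. It also conflicts with SAP 3.10, which moves incomplete onset dates to the day of treatment so that the event is treated as emergent.

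**The case against.** The case on the other side is substantial.

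- **The wordings may be one definition plus shorthand.** Protocol 11.1 and SAP 2.1 agree, Protocol 11.3.1 reads as a short restatement, and the synopsis may simply mean that the second implant was received. This is fair for implanted participants, but none of it brings in a surgery without an implant.
- **Analysing the implanted suits the objective,** which concerns AEs following bilateral implantation. It is a defensible set for that purpose. It still does not match a collection window that opens when surgery begins.
- **Nothing is hidden.** AEs are recorded, all form data are listed, and serious events are reported within 24 hours (Protocol 10.3). This stands: the loss is from the tabulated rates only.
- **The case may be rare.** Protocol 7.4 mentions duplicate implants supplied at surgery, which may make a procedure without an implant less likely. This also stands.

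A reader might go further and infer that explanted participants are dropped too. The documents do not support that. Protocol 11.1, Protocol 11.3.1 and SAP 2.1 turn on receiving the implant. Protocol 18.1 says of a participant who has the implant removed without withdrawing: "The participant would continue in the study with all planned follow-up visits and assessments". SAP 4.5.1 tabulates removals within the Safety Population. Only the undated verb in the synopsis leaves room for doubt.

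Nor should the 4 removals among 188 implanted subjects (Protocol 1.1.4) be used as a rate. All came after Month 24, so they say nothing about a six-month study or about abandoned surgery.

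**Conclusion.** The concern holds in a limited form. The only analysis set is worded inconsistently, and each wording makes membership depend on an implant having been placed, although AE assessment starts when surgery starts. If a surgery ends without an implant, its events would be listed but absent from the primary rates.

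The size cannot be estimated from the documents. The change from 1/31 to 0/30 assumes that exactly one such case occurs, that it involves a severe event and that there are no others. A reader might infer that the reported rates will be biased downward. The documents show only that they could be, since no such case is reported and no frequency is given. The explant question is confined to loose wording in the synopsis.

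The change is worth making because it is cheap and because one participant carries weight at this sample size.

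**What to change.** 1. Use one definition in the synopsis, Protocol 11.1, Protocol 11.3.1 and SAP 2.1: all participants in whom study-eye implant surgery was started, whether or not an implant was placed or later removed. Drop the condition of at least one safety measurement.
2. In SAP 4.3, count as treatment-emergent any event with onset from the start of surgery on Day 0, in line with Protocol 3 and 6.3.2. Without this, step 1 does not bring in intraoperative events.
3. In SAP 4.1, show counts of surgery started, implant placed, implant not placed and implant later removed.
4. Analyse participants without an implant on data from the visits they attend, as Protocol 11.3.1 already does for those who discontinue early.
5. If wanted, report serum CNTF and antibody results on the implanted subset.

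The cost is wording in both documents. AE rates may become slightly less favourable. Follow-up of any participant without an implant may be incomplete, because the post-surgery visits are currently described only for those who receive one.
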